4. OBJECTIVE AND ENDPOINTS

4.1. Objective

The primary objective is to investigate the immunological effect of Comirnaty by measuring the incidence of seroconversion (development of antibodies against SARS-CoV-2 upon vaccination in seronegative individuals) after 2 vaccine doses.

Secondary objectives:

- To evaluate safety and tolerability of the given vaccine in the research subjects.
- To measure the incidence of SARS-CoV-2 infection documented by a positive PCR test during the study period.

Exploratory objectives:

- Proportion (95% CI) seroconverting to a positive response to SARS-CoV-2 IgG serology after two doses of vaccine, at 9 months, 12 months, 18 months, 24 months, 30 months, and 36 months after the second vaccine dose. This may mean that patients in routine healthcare have received one or more additional vaccine doses depending on the recommendations of the Public Health Agency of Sweden.
- To investigate the humoral response in more detail and analyze the cellular immune response after the vaccine has been administered.
- To examine the virus genome in breakthrough infections of SARS-CoV-2.
- To evaluate the importance of the oral and intestinal microbiome for vaccine efficacy in HIV-infected individuals.

4.2. Endpoints

Primary endpoint:

- Proportion (95% CI) seroconverting to a positive response to SARS-CoV-2 IgG Serology test after two doses of vaccine, measured 2 weeks after the second vaccine dose.

Secondary endpoints:

- Proportion (95% CI) seroconverting to a positive response to SARS-CoV-2 IgG serology after two doses of vaccine, at 3 months and 6 months after the second vaccine dose.
- Proportion (95% CI) experiencing adverse events, with AE/SAE/SUSAR.
- Number and proportion (95% CI) who experience local reactions and systemic reactions.
- Proportion (95% CI) who receive a new diagnosis of SARS-CoV-2 infection through a positive PCR test.

Exploratory endpoints:

- Proportion (95% CI) seroconverting to a positive response to SARS-CoV-2 IgG serology after two doses of vaccine, at 9 months, 12 months, 18 months, 24 months, 30 months, and 36 months after the second vaccine dose. This may mean that patients in routine healthcare have received one or more additional vaccine doses depending on the recommendations of the Public Health Agency of Sweden.
- A more detailed description of humoral and cellular immune responses at baseline and after vaccinations in blood and saliva at time points immediately before the first vaccine dose (day 0), day 10 after the first dose, immediately before dose 2 on day 21, and 2 weeks, 3 months, 6 months, 9 months, 12 months, 18 months, 24 months, 30 months, and 36 months after the second vaccine dose.
- Prevalence of escape mutations in SARS-CoV-2 sequencing in breakthrough infections.
- Occurrence of development/progression of graft versus host disease in allogeneic stem cell transplant recipients.
- Occurrence of biopsy-verified rejection in solid organ transplant recipients.
- Occurrence of viremia (defined as HIV RNA >50 copies/mL) after vaccination in individuals with HIV infection.
- Change in HIV DNA from study start to 3 and 6 months, 9 months, 12 months, 18 months, 24 months, 30 months, and 36 months after the second vaccine dose in individuals with HIV infection.
- Association between oral and gut microbiome and vaccine response in HIV-infected individuals and controls.

5. STUDY DESIGN

5.1. Assessments and study procedures

5.1.1. Study participants

Immunosuppressed individuals (primary study population) and immunocompetent individuals (control population) are planned to receive two doses of the Comirnaty vaccine in an open-label cohort study without randomization or blinding. Study participants would have been offered vaccination within the Stockholm Region, regardless of whether they participated in the study or not.

A total of 540 individuals who wish to be vaccinated against COVID-19 are planned to be included in the study.

Within the primary study population of immunosuppressed individuals, 450 individuals are planned to be included. The goal is to include 90 individuals per patient category:

- Patients with primary
- immunodeficiency Patients with HIV
- infection
 - Patients who have undergone allogeneic stem cell transplantation/CAR T cell therapy
- Patients who have undergone solid organ transplantation Patients with
- chronic lymphocytic leukemia

We plan to include patient groups with both primary immunodeficiency and secondary immunodeficiency (HIV infection, allogeneic stem cell transplantation/CAR (chimeric antigen receptor) T cell therapy, solid organ transplantation, and chronic lymphocytic leukemia) among a large and heterogeneous group of all immunosuppressed patients in specialized care at the hospital. This is because these patient groups may be interesting to study from an immunological point of view, as different parts of the immune system are suppressed, and we have well-characterized patient groups at participating study units that are suitable for study. The patients attend regular check-ups at the outpatient clinic at Karolinska University Hospital and may form the basis for inclusion.

The control group (90 people in total) is planned to be recruited in the following age groups: 18-39 years (n=30), 40-59 years (n=30), and >60 years (n=30).

5.1.2. Test subject population

Recruitment of the primary population will take place at Karolinska University Hospital. For the patient group with primary immunodeficiency, an application for data extraction from the PIDcare quality registry (National Quality Registry for Primary Immunodeficiency Diseases) will be made to identify patients who can be included in the study. The data extraction will cover diagnosis and lab values (latest IgG, IgA, IgM, and lymphocyte profile).

The control group will be recruited, for example, from among staff at Karolinska University Hospital and, if necessary, from other healthcare units or facilities, such as primary care, via the Alltid öppet app, recruitment flyers, or advertising. Healthcare personnel are recruited as a control group because of easier access to sampling and because this is a priority group for vaccination among healthy individuals. Depending on when the study can start versus the vaccine rollout for healthcare personnel, others such as relatives of healthcare personnel or study participants may also be eligible for recruitment. The age category ≥ 60 years may be difficult to recruit among healthcare personnel, which is why external recruitment outside the hospital is necessary.

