5.3.2. Physical examinations

During the COVID-19 pandemic, physical outpatient visits for routine care at the hospital have been replaced with video visits or telephone contacts as much as possible to reduce the risk of exposure to SARS-CoV-2, especially for immunosuppressed patients who are also considered to be at higher risk of severe complications from COVID-19. This is therefore an established way of monitoring these patients in routine care. To reduce the risk of exposure to SARS-CoV-2, even when screening research subjects and during the study period, we plan to screen research subjects via video visits. During such a visit, electronic consent is planned to be obtained from the research subject and study doctor via an app, using an established and certified method, i.e. without a physical examination. However, screening via remote contact requires access to mobile Bank ID and a certain level of technical knowledge on the part of the research subject, which is why individuals (especially older individuals) who are unable or unwilling to have screening visits via remote contact in this manner will be offered a physical visit for screening. At both vaccination occasions, doctors will be on site who can perform a targeted and symptom-driven physical examination if necessary.

The rationale behind planning only targeted and symptom-driven physical examinations as needed during the study period is that we do not expect any specific side effects in the primary population related to Comirnaty, which is already an approved drug. In terms of side effects, it may rather be the opposite due to immunosuppression, with a lower frequency and severity of reactogenicity or autoimmune reactions as side effects of Comirnaty. Vaccination efficacy may prove to be suboptimal in this population, and patients therefore need to be protected from SARS-CoV-2 infection as much as possible, even in connection with measures taken in this study. The patients are well known to the clinics, where the usual follow-ups will take place within routine care during the study period. The most severely ill patients will continue to be closely monitored in routine care for their underlying disease, with physical examinations as needed in routine care.

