6.3.3. Analyses of secondary endpoints

- Proportion (95% CI) seroconverting to a positive response to SARS-CoV-2 IgG serology after two doses of vaccine, at 3 months and 6 months after the second vaccine dose, measured in the "two-dose vaccine population" compared with the control group.
- Proportion (95% CI) experiencing adverse events, with AE/SAE/SUSAR. Number and proportion (95% CI) experiencing local reactions and systemic reactions are measured in the "Full analysis set population".
- Proportion (95% CI) receiving a new diagnosis of SARS-CoV-2 infection through a positive PCR test is measured in the "Full analysis set population."

- Comparisons are made with the control group.

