6.4. Statistical methods

Continuous variables will be presented with mean and standard deviation [SD] for normally distributed values, and median and interquartile range (IQR) for non-normally distributed values. Categorical variables will be presented as frequency distributions.

Comparisons between patient groups and the control group will be made using the Chi-square test. P-values will be adjusted for multiple comparisons where necessary.

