Number of months after transplantation (most recent):

Induction treatment (No/yes - thymoglobulin/yes - dacluzimab)

Basic immunosuppression: (Cyclosporine A/Tacrolimus/Everolimus/Sirolimus)

Antimetabolite treatment: (Azathioprine/MMF)

Steroids: (Yes/No)

Rejection treatment <6 months (yes/no)

Rejection treatment <3 months (yes/no)

Thymoglobulin treatment in the past year (yes/no)

Rituximab treatment in the past year (yes/no)

Chemotherapy in the past year (no/yes, and if yes, which type?)

CMV/EBV/BK viremia in the last 3 months (yes/no)

Patient group 5. Patients with chronic lymphocytic leukemia

Rai stage (at start of vaccination)

- 0
- I
- II
- III
- IV
- UNK

Cytogenetics FISH (last performed, specify date):

- del(17p)/TP53 mutation (>10%)
- del(11q)
- trisomy 12
- del(13q)
- normal
- Not done

IgHV mutation status:

- Mutated
- Unmutated
- Not done

Previous treatment:

Yes/No Number of treatment lines:

Subgroups:

1. Indolent and untreated: Yes/No
2. Ongoing ibrutinib: Yes/No
Start date
Dose at inclusion in vaccine study: 140/280/420 mg/d

3. -FCR within the last 6-30 months: Yes/No
Start date
End date
-BR within the last 6-30 months: Yes/No Start date
End date
-Rituximab-containing treatment ongoing or within the last 6 months: Yes/No Date of last dose:

Own base module: Healthy controls

Gender:

M/F Age:

Diagnosis/es:

Medications in the last 4 weeks:

Current medications:

Ethnicity - Caucasian, Black, Oriental, Latino, other

BMI

Diet - normal diet/vegetarian/other

Antibiotic treatment in the last 3 months - yes/no, if yes, describe which antibiotic/duration

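### The unadjusted comparison of infection with controls mixes exposure with vaccine protection, because the first-named control source is hospital staff and exposure is not recorded

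*Combined protocol and SAP*

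**What the plan says.** **Endpoint and test.** New PCR-confirmed infection is a secondary endpoint (section 4.2). The objective behind it is worded as incidence: "To measure the incidence of SARS-CoV-2 infection documented by a positive PCR test during the study period" (section 4.1). Section 6.3.3 places it in the full analysis set ("Proportion (95% CI) receiving a new diagnosis of SARS-CoV-2 infection through a positive PCR test is measured in the" that population), and the list of secondary analyses ends with "Comparisons are made with the control group". Section 6.4 supplies the method: "Comparisons between patient groups and the control group will be made using the Chi-square test". Section 6 has no covariate, stratification, person-time or caveat on exposure for this endpoint.

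**Controls.** Section 5.1.2 names staff of the university hospital first, as an example, and explains: "Healthcare personnel are recruited as a control group because of easier access to sampling". Their priority for vaccination is the second reason. Other healthcare units, the app, flyers and advertising are allowed if needed, and relatives of staff or of participants may be eligible. For the 60-and-over stratum (30 of 90 controls, section 5.1.1), recruitment outside the hospital is called necessary.

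**Patients.** Section 5.2.1 replaces physical screening with video where possible, to reduce infection, with risk groups in mind. Section 5.3.2 says that "patients therefore need to be protected from SARS-CoV-2 infection as much as possible".

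**Data collected.** In Appendix 1, the list under "Own base module: Healthy controls" covers sex, age, diagnoses, medication, ethnicity, BMI, diet and antibiotics. Neither this list nor the patient modules contain occupation, patient contact, household or any other exposure item.

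**The concern.** A control group chosen for easy sampling can serve the seroconversion question, where the primary endpoint requires negative baseline serology and is read soon after dose 2. Infection differs, because it depends on how often a person meets the virus as well as on how well the vaccine protects. The groups are not randomised, and the protocol itself gives reason to expect unequal exposure: some controls work in a hospital, while the study tries to keep patients away from it.

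The synopsis describes protection of these patients against severe COVID-19 as a knowledge gap, so a tested patient-control difference in infection invites a reading as relative protection. If controls are more exposed, equal protection can look like fewer infections in patients, and worse protection can look like no difference or even an advantage. With no exposure item in the eCRF, the planned data cannot separate the two.

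**Working it through.** **1. The plan's own figure.** Section 6.1 claims power above 80% for N = 540, effect size 0.15 and alpha 0.05. Read as Cohen's w with 1 degree of freedom, the noncentrality is 540 × 0.15² = 12.15 and the power is 93.6%, which agrees. The statement concerns seroconversion only. No figure is given for infection, so there is none to reproduce.

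**2. Inputs.**
- From the documents: 90 controls; five patient groups of 90, or 450 pooled (section 5.1.1); chi-square test (section 6.4); alpha 0.05 (section 6.1).
- Assumed, because the documents give no values: control infection risk p; exposure ratio R (control exposure divided by patient exposure); susceptibility ratio S (patients' risk divided by controls' risk at equal exposure).

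**3. Formula.** Patient risk = p × S / R, so the observed risk ratio is S / R. Poorer protection (S > 1) is hidden when R = S and reversed when R > S. This needs no rate assumption beyond risks scaling with exposure. The probabilities below come from exact binomial enumeration of the two-sided 5% uncorrected chi-square test, without multiplicity adjustment.

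**4. Equal protection (S = 1).** At p = 20%, patient risk is 20/1.5 = 13.3%, 20/2 = 10% or 20/3 = 6.7%. At p = 10% it is 6.7%, 5% or 3.3%. Chance that patients are declared significantly lower:

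| Control risk | Layout (patients v controls) | R = 1.5 | R = 2 | R = 3 |
|---|---|---|---|---|
| 20% | one group, 90 v 90 | 22% | 47% | 77% |
| 20% | pooled, 450 v 90 | 39% | 73% | 95% |
| 10% | one group, 90 v 90 | 12% | 24% | 43% |
| 10% | pooled, 450 v 90 | 22% | 45% | 73% |

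At R = 1 the corresponding chance is about 2% to 3%.

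**5. Poorer protection hidden (S = 2, p = 20%).** At equal exposure the risks are 40% v 20%, and patients are declared significantly higher in 84% of trials (90 v 90) or 97% (pooled). With R = 2 the risks are 20% v 20%, and the chance of a significant result in the correct direction is about 2% in either layout.

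**6. Poorer protection reversed (S = 2, pooled).** With R = 3 the observed ratio is 2/3 = 0.67, and patients are declared significantly lower in 22% of trials at p = 10% and 39% at p = 20%. With R = 4 the ratio is 0.50, and the figures are 45% and 73%.

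**The case against.** **Control source.** A reader might infer that controls are mainly hospital staff. The documents do not support that. Staff are an example, no quota is set, other routes are open, and the oldest third needs outside recruitment. This dilutes any exposure gap: if that third had the same exposure as patients, an average R of 3 would need the other two thirds at x with (2/3)x + 1/3 = 3, so x = 4. The dilution weakens the larger ratios but leaves the point standing, since the mix is unrecorded and R = 1.5 already matters.

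**Patient exposure.** A reader might infer that patients are shielded and that the two arms have opposite exposure. Sections 5.2.1 and 5.3.2 describe remote visits and a need to protect patients. They do not describe behaviour in the community, and staff exposure to infection is never discussed. Higher exposure in controls is plausible but is an inference.

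**Purpose.** The objective is incidence, section 6.1 calls the study descriptive or exploratory, and no section says that the comparison estimates protection. The synopsis gap concerns severe disease, whereas the endpoint is any positive PCR, with severity graded separately. This stands as a limit on the harm. It also means that the objective can be met without a test against controls.

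**Size.** Section 6.4 speaks of patient groups against the control group, so 90 v 90 is the more faithful layout, and it gives the smaller figures. Section 6.4 also allows multiplicity adjustment where necessary, which would lower them further. The direction of the argument is unchanged.

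**Conclusion.** The point holds in limited form. As written, the plan gives an unadjusted contrast of infection between non-randomised groups whose exposure probably differs and is not recorded. A difference, or the lack of one, mixes exposure and vaccine protection in unknown proportion and cannot be read as relative protection. The stronger statement, that a difference would reflect exposure instead of protection, goes too far: the documents contain no exposure data, so neither the size nor the direction of the bias is known.

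The percentages rest on assumed control risks of 10% and 20%, assumed exposure ratios of 1.5 to 4, one exposure ratio for the whole control group, and complete follow-up of the planned numbers. They show that moderate exposure gaps are enough to mislead; they do not predict this trial's result. The problem concerns one secondary endpoint. The primary endpoint is little affected.

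**What to change.** 1. In section 6.3.3, take the infection endpoint out of the closing line on comparisons with the control group. Report it per group with a 95% confidence interval, and state that the groups may differ in exposure and that the figures do not compare vaccine protection.
2. Add one yes/no item on patient-facing health-care work to the patient base module and the healthy-controls module. It can be asked at an existing contact, for example the later follow-ups (sections 5.2.9 to 5.2.14), where participants are already asked about COVID-19. Show control infections split by it.
3. If a comparison is kept, stratify it by this item and state that household, community and precaution differences remain. The item reduces the confounding without removing it: most patients would probably answer no, so the controls outside health care would become the effective comparator.

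The cost is some wording, one eCRF item, and the loss of a p-value on a secondary endpoint, or small strata and less precision if the comparison is kept. Treatment, visits and sampling do not change.

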5.1.3. Inclusion criteria

1. Individuals who are ≥ 18 years old.
- 2a. Individuals with immunosuppressive disease who meet one of the following criteria:
 - Primary immunodeficiency

- HIV infection
- Review of allogeneic stem cell transplantation/CAR T cell therapy
- Review of solid organ transplantation
- Chronic lymphocytic leukemia

or

2b. Individuals without immunosuppressive disease or treatment who, in the investigator's opinion, have no significant co-morbidity.

3. Signed written consent to participate in the study.

5.1.4. Exclusion criteria

1. Previous or ongoing COVID-19.
2. Has coagulation disorders, other conditions associated with prolonged bleeding time, or anticoagulant treatments, which, according to the investigator, contraindicate intramuscular injection. Conditions that can be corrected with measures such as treatment with platelet concentrates, coagulation factors, or other measures for people on anticoagulants are not exclusion criteria.
3. Planned to receive another vaccine within 14 days prior to the first dose of the study vaccine, or during the period from the first dose of the study vaccine until 14 days after the second dose of the study vaccine, and vaccination with another vaccine that, in the investigator's opinion, cannot be planned outside these time periods.
4. Pregnancy or breastfeeding.
5. Hypersensitivity to the active substance or to any of the excipients contained in the vaccine.
6. Individuals who are unable to understand the research subject information. Individuals who, for other reasons, are deemed by the investigator to be unsuitable for inclusion.

5.2 Study procedures

5.2.1. Screening visit

Screening is done via video visit or as a physical visit. During the COVID-19 pandemic, the majority of routine visits for outpatients have been converted from physical visits to video visits/telephone contacts within routine healthcare, in order to reduce the spread and infection of SARS-CoV-2, especially for risk groups. Screening visits will therefore be conducted via video visits using the Alltid öppet app (used at Karolinska University Hospital for routine video visits), as far as possible. Mobile Bank ID is required to access Alltid öppet, and some IT knowledge is needed, so not all study participants will be able to use this.

Informed consent will be obtained during the screening visit. Electronic signing will take place via another app during video visits, and during physical visits, consent will be obtained via signing on paper.

The following procedures will be performed:

- Written/electronic informed consent.

- Demographic data will be collected, including baseline characteristics that may be relevant to underlying disease, co-morbidity, ongoing medication, and recently completed immunosuppressive treatments (within 4 weeks) (Appendix 1). Patient group-specific treatments prior to screening will be collected as described in 5.5.2. This includes a review of planned vaccinations with other vaccines within 14 days prior to the first dose of the study vaccine, or if another vaccine is planned to be administered during the period from the first dose of the study vaccine until 14 days after the second dose of the study vaccine. The investigator will assess whether this can be postponed so that no other vaccine is administered during the specified period.
- If the visit is a physical visit, a pregnancy test is performed using a urine sample for women of childbearing age at this time, otherwise it is performed on day 0.
- If the visit is a physical visit, clinical laboratory samples are taken (see Table 2 for specifications).
- If the visit is a physical visit, samples for HIV RNA and HIV DNA are taken, only for HIV-infected individuals.
- HIV-infected individuals and control subjects are offered participation in a study component investigating the significance of the microbiome for vaccine efficacy. Individuals who agree to participate in this component will be sent fecal sample collection kits to their homes after the video visit, or the kits will be given to them directly during the physical visit. The person can then send the fecal sample by mail to the study unit during the screening period, or drop it off on site on day 0, before or after the injection of the first vaccine dose. Saliva samples submitted in the study can be used for both antibody response and oral microbiome analyses.

5.2.2. Day 0

If study participants meet all inclusion criteria and no exclusion criteria, they can proceed to day 0, either on the same day or on another day within 28 days after screening. Day 0 visits take place at the study unit.

On day 0, the first vaccine dose is given according to the product summary, and the vaccination is registered in an internet-based reporting system for vaccinations according to healthcare routine (Vaccinera). The study unit where vaccinations are planned to be given will have the necessary equipment and medicines (adrenaline, cortisone, and antihistamine) on hand for a potential anaphylactic reaction. A doctor will be available.

Individuals with an increased risk of bleeding, such as known coagulopathy or anticoagulant treatments, will be managed according to section 5.3.1.

Day 0 samples will be taken before injection of the first dose of vaccine. Sampling according to the schedule in Table

2. For blood sample volume at each visit and total in the study for each subgroup of study participants, please see Appendix 2). Saliva will be collected by having study participants spit saliva into a clean jar for 5 minutes. It is also possible to provide a saliva sample after the vaccine dose.

Two groups of sampling are planned:

A. Group with sampling without cellular immunity.

B. Group with cellular immunity sampling (at least 40 study participants per patient group)

These two sampling groups are divided to give sampling group A participants the opportunity to also provide blood samples at sampling units at Karolinska University Laboratory (in addition to the study unit) during certain visits in the study (day 10 after the first dose, and 2 weeks, 3 months, and 6 months after vaccine dose 2). This is because it may be easier for these individuals to travel to these units for sampling. As all analyses of cellular immunity require sampling at the study unit, this may mean several visits to the unit for sampling group B patients (4 extra visits). The number of sampling occasions is the same for both groups, but the total blood volume throughout the study period is approximately 80 ml higher in sampling group B. Subgroups to these two groups (A and B) are whether the person is HIV-infected or not. This is because HIV RNA and DNA samples are taken from HIV-infected individuals at specific times. The amount of blood taken is up to 10 ml higher per sampling occasion for HIV-infected individuals than for other groups.

The diary that the study participant must fill in to monitor adverse events can either be completed in eDagbok via the Alltid öppet app or on paper, depending on what is possible for the study participant. This is due to the need for access to mobile Bank ID and certain IT skills required to use an app (e.g., difficulty for older people).

Sampling group A:

- Review of health declaration questions in Vaccinate, according to care routine before vaccination.
- Vital parameters: Blood pressure, pulse, temperature, and respiratory rate are measured. If the temperature is \geq 38 degrees, the study participant is rescheduled for the vaccine dose injection on another day, when the person has been fever-free for at least 48 hours.
- Review of new medications since the screening visit (except if the screening visit is on the same day as day 1). If the study participant has received any other vaccine within 14 days
- For women of childbearing age, a pregnancy test is performed using a urine sample if this has not been done during the screening visit.
- Sampling of clinical laboratory samples including blood count (hemoglobin, white blood cells, and platelets) and differential count (neutrophils, lymphocytes, monocytes, basophils, and eosinophils), liver function (ALT, AST, bilirubin, ALP), and creatinine, as well as IgG analysis, if not taken at the screening visit.
- Sampling for SARS-CoV-2 serology and more detailed analyses of humoral immunity (blood).
- Sampling for humoral immunity (saliva).
- Sampling for SARS-CoV-2 PCR test (nasopharynx, NPH).
- Fecal sampling for HIV-infected individuals and controls, for those who have agreed to this part and the sample has not been submitted after the screening visit.
- Sampling for HIV-RNA and HIV-DNA, only for HIV-infected individuals, if this has not been taken during the screening visit.

- Vaccine dose 1 is administered (unless contraindications have been identified following health declaration questions).
- Study participants remain at the healthcare facility for at least 15 minutes (30 minutes for those with bleeding disorders) after vaccination.
- A diary is given to the study participant/information about the eDiary.

Sampling group B:

- Review of health declaration questions in Vaccinate, according to care routine.
- Vital parameters: Blood pressure, pulse, temperature, and respiratory rate are measured. If the temperature is \geq 38 degrees, the study participant is rescheduled for the vaccine dose on another day, when the person has been fever-free for at least 48 hours.
- Review of new medications since the screening visit (unless the screening visit is on the same day as day 1).
- For women of childbearing age, a pregnancy test is performed using a urine sample if this has not been done during the screening visit.
- Clinical laboratory tests including blood count (hemoglobin, white blood cells, and platelets) and differential count (neutrophils, lymphocytes, monocytes, basophils, and eosinophils), liver function (ALT, AST, bilirubin, ALP), creatinine, and IgG analysis, if not taken at the screening visit.
- Testing for SARS-CoV-2 serology and more detailed analyses of humoral immunity (blood).
- Sampling for humoral immunity (saliva).
- Sampling for analysis of cellular immunity (blood).
- Sampling for SARS-CoV-2 PCR test (nasopharynx, NPH).
- Sampling of faeces for HIV patients and controls, for those who have agreed to this part and samples have not been submitted after the screening visit.
- Sampling for HIV-RNA and HIV-DNA, only for HIV patients if this has not been done during the screening visit.
- Vaccine dose 1 is given (unless contraindications have emerged after health declaration questions).
- Study participants remain at the healthcare facility for at least 15 minutes (30 minutes for haemophiliacs) after vaccination.
- A diary is given to the study participant/information about the eDiary.

5.2.3. 10-day follow-up (10-day FU) after the first vaccine dose (+/-3 days)

Sampling group A

All contact between study participants and study staff (research nurse or investigator) can be done remotely by phone or chat, if the Always Open function is available. Can also be done on site, if it coincides with the study participant's regular visit to the study unit or if the study participant prefers to be sampled at the study unit.

Blood samples can be taken at any of the Karolinska University Laboratory's sampling units in Stockholm, and saliva samples can be sent in a stamped envelope to the Karolinska Institute.

- Review of the diary (local and systemic reactogenicity).
- Review of adverse events (AE/SAE/SUSAR).
- Review of concomitant medication (all new drugs, including immunosuppressive/immunoglobulin treatments).
- Testing for SARS-CoV-2 serology and more detailed analyses of humoral immunity (blood).
- Sampling for humoral immunity (saliva).

Sampling group B

All procedures are performed at the study unit, as sampling for peripheral blood mononuclear cell (PBMC) samples is required for cellular immunity at the study unit:

- Review of the diary (local and systemic reactogenicity).
- Review of adverse events (AE/SAE/SUSAR).
- Review of concomitant medication (all new drugs, including immunosuppressive/immunoglobulin treatments).
- Sampling for SARS-CoV-2 serology and more detailed analyses of humoral immunity (blood).
- Sampling for humoral immunity (saliva).
- Sampling for analysis of cellular immunity (blood).

